2.2.1 Rationale for Dose Selection

Only patients who have been on a stable multiple daily insulin injections dose of NovoLog® or Humalog® and once daily basal Lantus® or Toujeo® for at least 3 months prior to screening will be included in the study. If required, patient dose should be adjusted during the 4-week run-in period to stabilize the patient dose. During the treatment period, dose adjustment should be avoided but it is permitted to ensure patient's stable state and safety.

3 OBJECTIVES AND ENDPOINTS

3.1 Objectives

3.1.1 Primary objectives

To demonstrate that immunogenicity as assessed by treatment emergent antibody response (TEAR) rate with MYL-1601D is equivalent to that of NovoLog® during 24-week treatment.

The TEAR rate will not be assessed in isolation but will be part of totality of evidence including changes in HbA1c, FPG, insulin dose, neutralizing antibodies and injection site reactions to ensure that changes in TEAR rate, if any, are clinically meaningful.

3.1.2 Other objectives

To compare MYL-1601D to NovoLog® administered in combination with Lantus®, with respect to:

- Immunogenicity assessments: visits TEAR assessments, incidences of Anti-Drug Antibody (ADA), positive insulin cross-reactive ADA, and positive Neutralizing Antibody (NAb)
- Analysis of impact of ADA on pharmacodynamic (PD) parameters such as FPG, HbA1c, and insulin dose.
- Incidence and rate of hypoglycemic events
- Occurrence of local reactions, systemic reactions and other adverse events
- Safety related to hypersensitivity and immune mediated adverse events (subgroup analysis)
- Change in HbA1c from baseline
- Change in fasting plasma glucose (FPG) from baseline
- Change in prandial, basal, and total daily insulin dose per unit body weight (U/kg) from baseline
- Change in 7-point SMBG profile from baseline
- Device-related safety assessment

3.2 Endpoints

3.2.1 Primary Endpoints

The TEAR rate during 24-week treatment period is the primary endpoint for this study.

TEAR is defined as either one of the following:

- 1) Subjects who are ADA negative at baseline and become positive at any timepoint post baseline
- 2) Subjects who are ADA positive at baseline and demonstrate 4-fold increase in titer values at any timepoint post baseline visit.

3.2.2 Secondary Endpoints

The secondary endpoint points are change from baseline to week 24.

3.2.2.1 Efficacy

- Change in HbA1c from baseline
- Change in fasting plasma glucose from baseline
- Change in prandial, basal and total daily insulin dose per unit body weight (U/kg) from baseline
- Change in 7-point SMBG profile from baseline

3.2.2.2 Safety

- Incidence of positive antibody response and NAb
- Impact of ADA on PD parameters, such as FPG, HbA1c, and insulin dose.
- Change in hypoglycemia rate (30 day adjusted) from baseline and incidence of hypoglycemic events.
- Incidence of treatment-emergent adverse events (TEAEs) and serious adverse events (SAEs).
- Incidence of local reactions (includes injection site reaction), systemic reactions.
- Incidence of hypersensitivity and immune mediated adverse events.
- Incidence of device-related safety assessment.

4 STUDY POPULATION

4.1 Study Population

A total of 500 subjects with T1DM are planned to be randomized in this study, to receive MYL-1601D or NovoLog® with a randomization ratio of 1:1.

A detailed description related to sample size determination is provided in [Section 7](#).

4.2 Inclusion and Exclusion Criteria

4.2.1 Inclusion Criteria

Subject eligibility should be reviewed and documented by an appropriately qualified member of the Investigator's study team before subjects are included in the study.

Subjects must meet all of the following inclusion criteria to be eligible for enrolment into the study:

1. Written and signed informed consent needs to be provided by subjects before starting any protocol-specific procedures.
2. Male and female subjects between the ages of 18 to 65 years, both ages inclusive.
3. Clinical diagnosis of type 1 diabetes mellitus for at least 6 months or more prior to screening.
4. Stable dose of once daily basal Lantus® or Toujeo® injection and multiple daily bolus NovoLog® or Humalog® injections for at least 3 months at screening.
5. Body mass index (BMI) of 18.5 to 35.0 kg/m² at screening (both values inclusive).
6. Stable weight, with no more than 5 kg gain or loss in the 3 months prior to screening (collected by subject interview during medical history).
7. Glycosylated hemoglobin (HbA1c) 6.5-10.0 % at screening.
8. Hemoglobin \geq 10.0 g/dL at screening.
9. Subject has the capability of communicating appropriately with the Investigator.
10. Subject is able and willing to comply with the requirements of the study protocol including the 7-point self-monitored blood glucose (SMBG), completion of subject diary records and following a recommended diet and exercise plan for the entire duration of the study.
11. Female subjects of childbearing potential who are willing to use oral contraception or acceptable methods of contraception, (e.g., intra-uterine device, spermicidal gel plus condom, diaphragm plus condom, etc.), from the time of screening and for the duration of the study, through study completion.
 - a. Periodic abstinence (e.g., calendar, ovulation, symptothermal, post-ovulation

methods) and withdrawal are not acceptable methods of contraception.

- b. Postmenopausal females must have had no regular menstrual bleeding for at least 1 year prior to screening.
- c. Female subjects who report surgical sterilization must have had the procedure at least 6 months prior to screening.
- d. All female subjects of childbearing potential must have negative pregnancy test results at screening and at clinic visits, as per the SCHEDULE OF ACTIVITIES (SOA).
- e. If female subjects have male partners who have undergone vasectomy, the vasectomy must have occurred more than 6 months prior to screening

4.2.2 Exclusion Criteria

Subject candidates must not be enrolled in the study if they meet any of the following criteria:

1. History or presence of a medical condition or disease that in the Investigator's opinion would place the subject at an unacceptable risk from study participation.
2. History of hypersensitivity to any of the active or inactive ingredients of the insulin/insulin analogue preparations used in the study, OR history of significant allergic drug reactions.
3. History of use of animal insulin within the last 2 years or use of approved or experimental biosimilar product or any experimental insulin at any time prior to study entry including MYL-1501D.
4. History of use of a regular immunomodulator therapy in the 1 year prior to screening.
5. History of autoimmune disorders other than T1DM or insufficiently treated autoimmune thyroid disorders judged clinically relevant by the Investigator (recorded while collecting subject history).
6. History of ≥ 1 episodes of diabetic ketoacidosis or emergency room visits for uncontrolled diabetes leading to hospitalization within the 6 months prior to screening.
7. History of clinically significant acute bacterial, viral or fungal systemic infections in the last 4 weeks prior to screening (recorded while collecting subject history).
8. Any clinically significant abnormality in electrocardiogram (ECG) or safety laboratory tests (LFT, RFT, hematology or any other laboratory deemed clinically relevant by the Investigator) conducted at screening and considered by the Investigator to make the subject ineligible for the study.
9. Serological evidence of human immunodeficiency virus (HIV), hepatitis B surface antigen (HBsAg) or hepatitis C antibodies (HCVAb) at screening (However, Subjects with confirmed inactive viral state can be included).

10. History of drug abuse, marijuana use, or alcohol dependence during the 1 year prior to screening.
11. Receipt of another investigational drug in the 3 months prior to screening (or as per local regulations), or if the screening visit is within 5 half-lives of another investigational drug received (whichever is longer), or scheduled to receive another investigational drug during the current study period.
12. Subjects with the following secondary complications of diabetes:
 - a. Active proliferative retinopathy as confirmed by a dilated ophthalmoscopy examination / retinal photography (performed by a person legally authorized to do so) within the 6 months prior to screening.
 - b. Clinical nephrotic syndrome or diabetic nephropathy with a serum creatinine level >1.5 times of upper limit of reference range at screening
 - c. History of severe form of neuropathy or cardiac autonomic neuropathy, recorded while collecting subject history. Subjects with mild or moderate forms of neuropathy will be allowed.
 - d. Subjects with a history of limb amputation as a complication of diabetes (at any time), or any vascular procedure during the 1 year prior to screening.
 - e. History of diabetic foot or diabetic ulcers in the 1 year prior to screening.
13. Any elective surgery requiring hospitalization planned during the study period.
14. Clinically significant major organ disorder at the time of screening including:
 - a. Uncontrolled hypertension, defined as stage 2 hypertension by Joint National Committee VII (even if therapy is ongoing, blood pressure \geq 160 mm Hg systolic or \geq 100 mm Hg diastolic).
 - b. Uncontrolled hyperthyroidism or hypothyroidism (subjects can be included if these conditions are controlled with thyroid hormones or anti-thyroid drugs).
 - c. History of impaired hepatic function which is seen in the screening laboratory test and is judged by the investigator to be clinically significant - alanine transaminase [ALT] or aspartate transaminase [AST] value >2 times the upper limit of the reference range and/or serum bilirubin 1.5 times the upper limit of the reference range at the screening visit. Subjects with evidence of Gilbert's disease may be included in the study if they have total bilirubin of <3 mg/dL with indirect bilirubin contributing to >80% of the total bilirubin.
15. History of a significant medical condition, such as:
 - a. Clinically significant cardiac disease like unstable angina, myocardial infarction, grade 3 or 4 congestive heart failure (CHF) according to New York Heart Association criteria, valvular heart disease, cardiac arrhythmia requiring treatment, and pulmonary hypertension; during the year prior to screening.

- b. Stroke or transient ischemic attack (TIA) in the 6 months before screening.
16. Subjects with major depressive illness in the last 3 years (those who have well-controlled depression for 3 months on a stable dose of antidepressants, and have not experienced a major depressive episode in the last 3 years, can be included, even if they are on medication), subjects with history of other severe psychiatric diseases (manic depressive psychosis [MDP], schizophrenia), which in the opinion of the Investigator precludes the subject from participating in the study (recorded while collecting subject history).
 17. History of hematological disorders that can affect the reliability of HbA1c estimation (hemoglobinopathies, hemolytic anemia, sickle cell anemia, etc.).
 18. Subjects using the following in the 3 months prior to screening:
 - a. Insulin pump therapy
 - b. Any anti-diabetic drugs other than the study insulins allowed by the protocol.
 19. Moderate insulin resistance, defined as requiring total insulin of ≥ 1.5 U/kg/day.
 20. Subjects who have received ≥ 14 consecutive days of glucocorticoid therapy by oral, intravenous, inhaled or other routes that produce systemic effects within the past 3 months, or who have received steroids by any route (except intra-nasal, intra-ocular, and topical) within the 4 weeks immediately preceding screening.
 21. Subjects diagnosed as having cancer (subjects with history of basal cell carcinoma, carcinoma in situ or squamous cell cancer of skin, or in remission > 5 years, will be allowed).
 22. Subjects who have donated blood or plasma in the 1-month prior to screening.

4.2.3 Criteria for Early Termination or Discontinuation

Subjects can decide to discontinue entirely from the study at any time for any reason, this is documented as withdrawal of consent. Subjects can decide to discontinue from the study treatment at any time for any reason, but may choose to remain in the study for off-treatment study visits. Subjects can also be discontinued from the study or discontinued from the study treatment due to Investigator or Sponsor decision as detailed below.

The Sponsor or their representative must be notified by the Investigator as soon as possible, and prior to the early termination visit, on the decision to discontinue the subject from the study or from study treatment and provide detailed information on the reason/event.

In case of discontinuation of the subject from the study, an early termination visit (outlined as an End of Treatment visit in the Schedule of Activities) is required immediately and the site must complete the End of Study eCRF data. In case of the discontinuation of the subject from the study treatment, the subject is required to complete the End of Treatment visit, switch to marketed treatment (both basal and bolus treatments) and agree to proceed with the scheduled visits/activities.

The reason for discontinuation should be established based on the following reasons and recorded.

The following are reasons for discontinuation:

1. Withdrawal of consent.
2. For female subjects, diagnosis of pregnancy or stated intention to become pregnant. In this case subjects should be discontinued from the study (early termination visit is done immediately). Effort should be made by the site to obtain consent from the pregnant women, so that they are followed until delivery or termination.
3. At the Investigator's discretion (following discussion with the Sponsor medical monitor), for safety issues such as severe hypoglycemia or hypoglycemic unawareness. In this case subjects can be discontinued from the study (early termination visit is done immediately) or discontinued from the study treatment and continue with the study visits and procedures with marketed treatment (no need to perform early termination visit as subject proceed with the scheduled visits). The site should request the subject consent to follow-up as per the SCHEDULE OF ACTIVITIES until the Week 28 (Follow-up visit).
4. At the Investigator's discretion (following discussion with the Sponsor medical monitor), in certain situations such as lack of compliance, significant illness, hospitalization for surgery, or an SAE. In this case subjects can be discontinued from the study (early termination visit is done immediately) or discontinued from the study treatment and continue with the study visits and procedures with marketed treatment (no need to perform early termination visit as subject proceed with the scheduled visits).
5. Sponsor terminate the study due to safety issues. In this case subjects should be discontinued from the study (early termination visit is done immediately).

Subjects who decide to discontinue from treatment and agree to remain in the study, on marketed treatment, are required to adhere to the study protocol, thus perform all activities and procedures such as SMBG measurements, completing diary entries, participating in their regularly scheduled study visits for completion of all assessments and procedures as outlined in the Schedule of Activities until the Week 28 (Follow-up visit).

If the subject withdraws from the study and also withdraws consent for disclosure of future information, no further evaluations should be performed and no additional data should be collected. The Sponsor may retain and continue to use any data collected before such withdrawal of consent.

The site should explain the subject the importance of data collection and make every effort to consent the subject to continue follow up per the SCHEDULE OF ACTIVITIES until Week 28 (Follow-up visit).

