8. Immunogenicity samples: At Visits 1, 6, 8, 9, 10, 11, 12, 13 and 15. At each visit, five blood samples of 5 mL each (25 ml per visit) will be drawn for ADA and NAb.
9. V15 is regard as Early Termination from Treatment visit or Study End of Treatment visit. In case the subject discontinues treatment early, the site should explain the importance of data collection and make every effort to retain the subject, perform the remaining visits, off study treatment, per the SCHEDULE OF ACTIVITIES, up to the completion of Week 28/Follow-up call.
10. BMI is calculated at screening visit, randomization visit, week 12 and week 24.

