- Review current dosing of MYL-1601D or NovoLog® and Lantus® and if necessary provide new dosing instructions and document the new dose and reason for change.
- Review subject diary and provide information regarding the completion requirements and necessary glucose measurements provided.
- Dispense study medication MYL-1601D or NovoLog® and Lantus®, except for Visit 8.
- Perform drug accountability and check for treatment compliance.
- Dispense diary.

6.3.4 Visit 15/Early Termination from Treatment/Study Termination/ End of Treatment (EOT, Week 24)

During this visit, the following procedures and assessments will be performed:

- Discuss and check compliance to standard of care specifics as per American Diabetes Association 2019 guidelines, self-management of diabetes and life-style modifications with the subject.
- Record body weight and calculate BMI.
- Record concomitant medications since previous visit.
- Record vital signs (sitting after 5 minutes rest; pulse, blood pressure, temperature and respiratory rate).
- Perform and document physical examination.
- Perform 12-lead ECG (supine, after 5 minutes rest) and document results.
- Record AEs, SAEs, local and systemic allergic reactions and hypoglycemic events since the previous visit.
- Record device complaint.
- Collect blood and urine samples for the following laboratory assessments:
 - Urine pregnancy test for women of childbearing potential
 - Fasting plasma glucose
 - HbA1c
 - Hematology
 - Blood chemistry
 - Urine analysis
 - Fasting lipid profile
 - Immunogenicity analysis (collect blood sample prior to study drug administration)
- Review diary, 7-point SMBG measurements, performed on 3 days during the week prior to the visit.
- Review current dosing of MYL-1601D or NovoLog® and Lantus®.
- Subject should be instructed on the switched to the marketed products; dosing and administration instructions.

- Collect all study materials for last study treatment visit (in case of Early Termination from Treatment/End of Treatment). In case subject is discontinued from the study treatment but agrees to continue and perform the study visits and procedures the materials will be kept until the subject last visit to the site which is visit 15.
- Perform drug accountability and check for treatment compliance.

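### The protocol both requires and waives the End of Treatment visit for subjects who stop study drug but stay in the study, so assessments scheduled only at V15 can be deferred to Week 24

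*Protocol*

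**What the plan says.** **The requirement.** Protocol 4.2.3, third paragraph: "In case of the discontinuation of the subject from the study treatment, the subject is required to complete the End of Treatment visit". Section 6.3.5 repeats the sentence. Neither place states an exception.

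**The waiver.** Reason 3 of 4.2.3 covers safety issues such as severe hypoglycemia. Reason 4 covers non-compliance, significant illness, hospitalization for surgery or an SAE. For a subject who stops study treatment under either reason but stays in the study, the text reads: "no need to perform early termination visit as subject proceed with the scheduled visits".

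**The visit itself.** For a subject leaving the study, 4.2.3 says "an early termination visit (outlined as an End of Treatment visit in the Schedule of Activities) is required immediately". Table 1 footnote 9 adds: "V15 is regard as Early Termination from Treatment visit or Study End of Treatment visit".

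**Study materials.** Section 6.3.4 first says "Collect all study materials for last study treatment visit (in case of Early Termination from Treatment/End of Treatment". For subjects who stop treatment but carry on with study visits, it then says "the materials will be kept until the subject last visit to the site which is visit 15".

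**Analysis.** SAP 8.1 enters early termination data under Visit 14, labelled week 18, and moves them for summary tables to the next planned visit. When a visit has several records, the latest is analysed.

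**The concern.** Two sites with identical subjects could act differently and both cite the protocol. One would run the V15 procedures when treatment stops; the other would run none of them until Week 24. The waiver covers subjects stopped for severe hypoglycemia or an SAE, for whom laboratory, ECG and examination findings at stopping are of particular interest.

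There is also an analysis problem. The only post-baseline safety laboratory value for such a subject may be a Week 24 value taken on marketed insulin, yet it enters the comparison by arm in SAP 8.9.1 with nothing to mark it as off drug. This can happen even at a site that does the stopping visit, because of how SAP 8.1 assigns it.

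**Working it through.** **1. Are the two visits the same?** Section 4.2.3 defines the early termination visit as the schedule's End of Treatment visit. Footnote 9 makes V15 serve both purposes, and the heading of 6.3.4 groups early termination from treatment, study termination and End of Treatment under V15. The procedures required in one place are therefore those waived in another.

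**2. What does the waiver defer?** From Table 1:

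| Assessment | Scheduled at |
|---|---|
| Hematology, chemistry, urinalysis | V1, V6, V15 |
| Physical examination | V1, V6, V15 |
| Fasting lipids | V6, V15 |
| 12-lead ECG | V1, V15 |

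After baseline, each occurs only at V15.

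**3. For how long?** Deferral = 24 − week of stopping. The time axis agrees with the protocol's own figure: Week −7 to Week 28 is 35 weeks, the stated maximum study duration.

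| Treatment stopped at | Weeks to V15 |
|---|---|
| Week 1 call | 24 − 1 = 23 |
| Week 2 | 24 − 2 = 22 |
| Week 4 | 24 − 4 = 20 |
| Week 12 | 24 − 12 = 12 |
| Week 20 | 24 − 20 = 4 |

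There is no earliest stopping time: "Subjects can decide to discontinue from the study treatment at any time for any reason". The nominal ceiling is therefore just under 24 weeks. With the widest visit windows (V6 on day −3, V15 on day 175) it is (175 + 3)/7 = 25.4 weeks.

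**4. What continues?** Section 6.3.3 keeps on-site visits at Weeks 2, 4, 8, 12, 16 and 20. Each records AEs, SAEs, hypoglycemic events, vital signs and weight and takes immunogenicity samples. Fasting plasma glucose is measured from Week 4 and HbA1c at Week 12. The longest gap between successive on-site visits is 28 days nominally, or 42 days with windows (for example V10 on day 49 to V11 on day 91).

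**5. What does the SAP do with a stopping visit?** In Table 1 and in SAP 8.1's own window table, V14 is at Week 22, not week 18; Protocol 6.3.2 makes it a telephone contact. SAP 8.1's worked example sends a subject stopping at Visit 9 to Visit 10 for fasting glucose and to Visit 11 for HbA1c, that is, to the next visit at which that test is planned. For safety laboratory tests that visit is V15. A subject who stays in the study also has a true Week 24 sample, so two records compete for V15 and the later, off-drug one is used. SAP 8.1 also lets end of treatment data fill a scheduled visit only when the scheduled value is missing, which again favours Week 24.

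**The case against.** **Reasons 3 and 4 may be deliberate exceptions.** The third paragraph can be read as a general rule with specific exceptions below it. It also uses different names, an early termination visit for leaving the study and an End of Treatment visit for stopping treatment, and only the first is waived. Neither reading settles the matter. The requirement is unqualified in two sections, 6.3.5 points to 4.2.3 only for the reasons for stopping, and the two names are defined as the same procedures. If an exception is intended, the text should say so.

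**A reader might infer that safety checking lapses after stopping.** The documents do not support that. On-site visits continue, reported symptoms are evaluated (6.5.2.1), AEs are followed to resolution or stability (9.3.2.7), and SAEs are notified within 24 hours (9.3.2.8). Only the V15-only items are deferred.

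**A reader might infer that 6.3.4 contradicts itself on materials and leaves study insulin pens at home.** The two sentences read as a rule followed by an exception. Subjects who stay in still need the glucometer and diary. Study materials are not defined, and the text does not say who keeps them. Whether unused study insulin is included is unclear; that is an ambiguity. Drug accountability also continues at on-site visits.

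**The statistical consequence is limited.** This stands for the primary endpoint: ADA sampling continues, and Protocol 7.2.2 includes post-discontinuation data. ECG parameters and examination results are not recorded in the CRF (6.5.2.6, 6.5.2.8), so flagging them value by value would not fit. SAP 8.1 does have a mapping rule, but that rule produces the displacement shown above.

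**Conclusion.** The conflict over the End of Treatment visit is real and needs reconciling. For subjects stopped under reasons 3 or 4 who stay in the study, physical examination, ECG, safety laboratory tests and lipids may be done at stopping or deferred to Week 24, depending on which sentence the site follows. Deferral is 22 weeks from a Week 2 stop, 12 weeks from a Week 12 stop, and nominally just under 24 weeks at most. AE, hypoglycemia and vital-sign checks continue meanwhile. The materials text is ambiguous about study insulin.

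On the analysis side, the effect is confined to by-visit laboratory summaries and models, where an off-drug Week 24 value can displace the value at stopping. This assumes that the mapping in SAP 8.1 follows its own fasting glucose and HbA1c example. The number of subjects affected is not given in the documents and cannot be derived from them. The primary TEAR analysis is not put in doubt by this point.

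**What to change.** **Protocol.** Reconcile 4.2.3 (third paragraph, reasons 3 and 4), 6.3.5 and Table 1 footnote 9 so that they state one consistent policy on the visit when treatment stops, including any intended exceptions. In 6.3.4, define study materials, say whether unused study insulin is included, and say who keeps them. The sponsor's clinical team decides which rule stands.

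**SAP.** In 8.1, correct the reference to Visit 14 at week 18. Give the End of Treatment visit at stopping its own analysis visit code, so that Week 24 laboratory values do not replace its values. In 8.9, flag each laboratory value as on or off assigned drug.

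**Cost.** A protocol clarification, a letter to sites and minor programming. If the sponsor keeps the requirement, a few subjects have one extra visit, made up of assessments already in the protocol. If the sponsor keeps the waiver, no scheduled on-drug laboratory value after baseline will exist for those subjects; the flag would make that visible but cannot supply the value.

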5.5 Breaking the Blind

The trial design is open-label since the two products, MYL-1601D and NovoLog®, have distinct packaging. To avoid any bias in the evaluation of the critical endpoints, a blinded analysis of immunogenicity and other parameters such as HbA1c and FPG is planned. In addition, the majority of the study personnel (Sponsor and select CRO staff) will be blinded to the randomized assigned treatment arms and this will be documented, listing the Sponsor and CRO personnel who are unblinded to ensure transparency and proper study conduct.

As all Investigators and sites staff are not blinded to treatment, no process required for breaking the blind.

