5.7 Rescue Criterion

The following rescue criterion will be implemented to protect the safety of subjects during the study:

“Worsening of HbA1c by >1.0% compared to baseline at 12 weeks post randomization”.

At the week 16 (Visit 12) study visit, if the subject meets the rescue criterion above, the Investigator can decide to proceed with one of the following options;

- 1) continue the study with no drug change
- 2) continue the study and adjust the dose of the study treatment
- 3) discontinue from the study treatment and switch to study NovoLog® if the subject is assigned to MYL-1601D
- 4) discontinue from the study treatment if the subject is already assigned to NovoLog® and switch to marketed treatment (both basal and bolus treatments)
- 5) early termination from the study

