The primary analysis will be based on the ITT analysis set. In addition, all post-discontinuation and rescue data should be included in the analysis. Further analysis details analysis steps and example SAS codes will be provided in the SAP.

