7.4 Analysis Set Definitions

The ITT analysis set includes all randomized subjects (including subjects who receive incorrect treatment, do not complete the study or do not comply with the protocol or used prohibited medication).

The PP analysis set includes subjects who complete Week 24 and do not have protocol violations that impact the primary outcome (as detailed in the statistical analysis plan).

Subjects who take other fast acting insulin other than assigned study medication such as rescue medication will be excluded from PP analysis set. The subjects excluded from the PP analysis set will be identified before database lock (i.e., before unblinding the study team).

The safety analysis set includes subjects who take at least one dose of the study medication after randomization. For safety analyses, subjects will be categorized according to the treatment that they actually received.

Run-in analysis set includes all subjects who enrolled into run-in period.

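### Protocol 4.2.3 (reasons 3 and 4) and option 5 of 5.7 let an unblinded investigator end a subject's follow-up, not only study drug, without withdrawal of consent, so TEAR data are lost avoidably

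*Protocol*

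**What the plan says.** **Exits.** Protocol 4.2.3 lists withdrawal of consent as reason 1, separate from the investigator-led reasons. Reasons 3 and 4 both open with "At the Investigator's discretion (following discussion with the Sponsor medical monitor". Reason 3 applies "for safety issues such as severe hypoglycemia or hypoglycemic unawareness. In this case subjects can be discontinued from the study". Reason 4 covers situations "such as lack of compliance, significant illness, hospitalization for surgery, or an SAE. In this case subjects can be discontinued from the study". Each also offers the alternative of stopping study treatment and continuing the visits on marketed insulin. Nothing says when removal is needed instead of that alternative. Option 5 of 5.7, available at Week 16 to a subject who meets the rescue criterion, is "early termination from the study".

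**Who decides.** Protocol 5.5: "As all Investigators and sites staff are not blinded to treatment, no process required for breaking the blind".

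**What the analysis wants.**
- Protocol 7.2.2: "all post-discontinuation and rescue data should be included in the analysis".
- The ITT set in 7.4 keeps subjects who "do not complete the study or do not comply with the protocol".
- Table 1 footnote 9, for subjects who stop treatment early, tells sites to "make every effort to retain the subject, perform the remaining visits, off study treatment".
- TEAR counts a response at any post-baseline visit (3.2.1).
- With at least 6 retrieved dropouts per arm, missing values are modelled from them; otherwise all non-missing subjects in the same arm are used (Protocol 7.2.2; SAP 7.2.1 and 8.7.2.1).
- The sample size makes no allowance for attrition (7.1).

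**The concern.** None of the listed reasons is a withdrawal of consent, so in many cases sampling could go on. Each removal ends the scheduled ADA samples for an endpoint that counts any visit. It also costs one potential retrieved dropout, which can take an arm below 6 and switch the primary imputation to its fallback. Because sites know the treatment, the choice between the two routes could differ by arm.

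At stake is the direction of any error. Suppose subjects removed for illness, an SAE or hypoglycemia would have turned TEAR positive more often than those kept, and suppose they are imputed from those kept. The rate in that arm is then understated. If this happens mainly in the MYL-1601D arm, a true excess looks smaller and equivalence is easier to declare.

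**Working it through.** **1. The plan's own figure.** Protocol Table 5 gives 80% power with 250 per arm. The margin formula (SAP 8.7.2.1, with the quantiles coded in SAP 10.2) is (1.645 + 1.282) × √(2p(1−p)/250).
- p = 10%: 2.926 × √(0.18/250) = 7.85 points (Table 5: 7.9).
- p = 30%: 2.926 × √(0.42/250) = 11.99 points (Table 5: 12.0).

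All twelve margins agree within 0.05 points, and power at a true difference of zero is 79.5% to 80.6%.

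**2. Who becomes missing.** Removal requires an immediate early termination visit (4.2.3), and that visit includes an immunogenicity sample (6.3.4). A subject who already meets the TEAR criteria is not counted as missing (7.2.4; SAP 7.2.1). What remains is the subject with undetermined status at exit. Bias comes from those who would have converted later.

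**3. Bias if loss falls on one arm.** The documents give no removal rate, so these inputs are assumptions: a share f = 5% of the MYL-1601D arm (12-13 of 250) is removed with undetermined status; their eventual TEAR rate r is 1.5 to 2 times the arm's rate, capped at 100%; they are imputed at the retained-subject rate; NovoLog loses none. The true difference is set equal to the Table 5 margin.

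Seen MYL-1601D rate = (true rate − f × r)/(1 − f).

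Example, reference 20%, margin 10.5 points, true MYL-1601D rate 30.5%:
- r = 45.75%: (0.305 − 0.05 × 0.4575)/0.95 = 29.7%, a shift of −0.8 points.
- r = 61%: (0.305 − 0.05 × 0.61)/0.95 = 28.9%, a shift of −1.6 points.

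The chance of passing was then computed exactly from two binomials (n = 250 each), with the 90% Wald interval and the margin evaluated at the observed NovoLog rate.

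| Reference rate | Margin (points) | Shift (points) | Pass, no loss | Pass, 5% removed |
|---|---|---|---|---|
| 5% | 5.7 | −0.3 to −0.6 | 9% | 10-12% |
| 10% | 7.9 | −0.5 to −0.9 | 7% | 9-12% |
| 20% | 10.5 | −0.8 to −1.6 | 6% | 9-13% |
| 30% | 12.0 | −1.1 to −2.2 | 6% | 9-14% |
| 50% | 13.1 | −1.7 to −1.9 | 5% | 10-11% |

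At reference rates of 35% and 40% the upper value is just under 15%. The no-loss column exceeds 5% because the margin moves with the observed NovoLog rate; with the margin held fixed it is 5.0%. If r equals the arm's rate, the formula gives a shift of zero.

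**4. Loss without bias.** Equal loss in both arms, no information recovered, fixed Table 5 margin: power falls from about 80% to 77-78% at 5% loss and 74-75% at 10%.

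**5. Outer bound.** Each 1% of one arm with undetermined status can move the difference by at most 1 point, which is 8% to 13% of the margin at reference rates of 10% to 50%.

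**The case against.** Much of the opposing case stands.

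- **Contradiction.** A reader might infer that the exit option contradicts the analysis. It does not, strictly. Footnote 9 concerns subjects who stop treatment, the ITT definition expressly foresees non-completers, and 7.2.2 says to use post-discontinuation data without promising that everyone will have them. The fit is poor, but the texts can be read together.
- **Unchecked discretion.** This is not in the text either. The medical monitor must be consulted and the Sponsor notified with reasons before the exit visit, although no approval is stated. Reason 3 also has the site request consent to follow-up to Week 28, and 4.2.3 ends with a general retention instruction. Neither takes the option away.
- **Hidden false equivalence.** One planned analysis sets missing MYL-1601D subjects to TEAR positive and imputes nothing for NovoLog (7.2.4; SAP 8.7.2.2). A tipping-point analysis covers every split of the missing outcomes (SAP 8.7.2.3). A result that depends on these losses would show. The analyses do not prevent the loss, and equivalence is declared on the primary analysis.
- **Size.** Assuming that 40-60% of removed subjects would be positive gives pass chances above 20%, up to about 35%, at a 5% reference rate. That is 3.7 to 5.6 times the arm's own 10.7%, which nothing in the documents supports. Under the same assumption the shift is only +0.1 to −0.95 points at a 30% reference rate, and at 50% it reverses (+0.2 to +1.2 points).
- **Imputation.** With 6 or more retrieved dropouts per arm, the model is not based on retained subjects as assumed above.
- **Feasibility.** Serious illness or hospitalization can make visits impossible, so a flat ban on removal would go too far.

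**Conclusion.** The point holds as an avoidable weakness of modest size. The protocol lets an investigator who knows the arm, after discussion with the medical monitor, end follow-up in a subject who has not withdrawn consent. That costs primary-endpoint samples and potential retrieved dropouts.

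Under one-arm loss of 5%, 1.5 to 2 times the arm's TEAR rate among those removed, and imputation at the retained-subject rate, the chance of a wrong equivalence claim at the margin goes from about 5-9% to about 9-14% at the five tabulated reference rates. All three inputs are assumptions. Without the excess positivity the bias disappears and only the loss of data remains. That removal will in fact differ by arm is a further inference the documents do not support: open-label conduct makes it possible, and no more can be said.

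**What to change.** In Protocol 4.2.3, reasons 3 and 4, state that these reasons lead to discontinuation of study treatment only. Scheduled visits and ADA sampling then continue to Week 24 unless the subject withdraws consent or follow-up is not feasible, with the reason documented. Reconcile option 5 of 5.7 with this wording. Whether study treatment is stopped, and how the subject is then treated, stays as written.

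The cost is protocol wording in two sections and a few more off-treatment visits, all already in the schedule. The sample size of 500 and the planned analyses do not change.
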